11.4.4 Handling of Missing Data

Interim Analysis:

At the time of each interim analysis, some subjects will not have completed the full 30-day follow-up for their safety evaluation. The number of failures for the primary safety endpoint in subjects with incomplete information will be assumed to follow a beta-binomial distribution. The predicted number of failures for the primary safety endpoint will be estimated from these beta-binomial distributions for estimating the predictive probability of success for the safety endpoint.

Final Analysis:

The reasons for missingness, if available, will be listed for subjects with missing data. Patients with missing effectiveness data will be excluded from the primary effectiveness analysis.

Subjects without full follow-up required per protocol for the safety endpoint assessment will be excluded in the primary analysis unless they have experienced a PAE. Sensitivity analyses for missing data will be performed to assess the impact of missing values on the primary safety outcome and are described in the section 11.4.5.

11.4.5 Sensitivity Analyses

To investigate the robustness of the primary safety endpoint results, the following sensitivity analyses will be performed.

1) Tipping Point Analysis in mITT Population

In this study, the tipping point is defined as the number of subjects with primary AEs for the binary safety endpoint in the study population at which the study conclusion is changed. The tipping-point analysis will replace the missing values with primary AE occurrence one at a time and the corresponding exact one-sided 95% upper confidence bound will be produced³. The confidence bound is calculated to test the PAE rate against the performance goal of 15%. If the exact one-sided 95% upper confidence bound calculated based on the imputed number of PAEs leads to a change in the study conclusion, then the imputed number of PAEs will be considered the tipping point.

The tipping-point analysis for binary safety endpoints will analyze all possible cases that may occur in the missing data cohort. The results will be presented in a summary table to illustrate how the exact one-sided 95% upper confidence bound and the conclusion on meeting the performance goal change.

2) Primary Safety Analysis in Safety Population

The primary safety analysis will be repeated in the Safety Population to include all enrolled subjects who had study catheter inserted in the evaluation of safety. The analysis is based upon data available and the early onset PAEs will be carried forward. The exact binomial proportion will be presented together with the one-sided 95% upper bound of the confidence interval.

To investigate the robustness of the primary effectiveness endpoint results, the primary effectiveness analysis will also be performed in the Safety Population for all enrolled subjects who had study catheter inserted and RF delivered with study catheters. The analysis is based upon data available. The exact binomial proportion will be presented together with the one-sided 95% lower bound of the confidence interval.

11.4.6 Subgroup Analyses

Summary statistics and listings of the primary safety and effectiveness endpoints will be presented by the following factors:

- Age group: <60 vs. ≥60 years
- Repeat procedure during blanking period: Repeat procedure conducted vs. Not conducted
- Study Site
- Sex
- Operator's ablation procedure experience level: More experienced (participated in RADIANCE study or balloon experience ≥15 cases per year) vs. Less experienced (balloon experience <15 cases per year)

Subgroup analyses will be performed in the PP population for the primary effectiveness endpoint and in the mITT population for the primary safety endpoint.

11.5 Analysis of Secondary Endpoints

No formal statistical hypothesis and inferential statistics will be formulated and performed for the secondary endpoints. Analyses of all secondary endpoints will be performed descriptively in the proposed analysis populations excluding the subjects with missing outcomes.

11.5.1 Secondary Safety Analysis

The PAE will be summarized by the individual type of composite. Serious AEs will be summarized by the relationship to the device (SADEs) and to the procedure and by three timeframes (ablation to ≤7 days, >7 to 30 days, and >30 days post ablation). Hospitalization for cardiovascular events, which cause prolonged stay ≥2 nights post index procedure or in-patient stay not concurrent with index procedure ≥ 1 calendar day, will be summarized. Non-serious AEs will be summarized descriptively.

These analyses of secondary safety endpoints will be performed in the SP, mITT population and roll-in subjects.

11.5.2 Secondary Effectiveness Analysis

11.5.2.1 Secondary Effectiveness Endpoints of Effectiveness Success

Secondary effectiveness endpoints, including 6-Month Effectiveness Success and 12-Month Effectiveness Success will be summarized descriptively for all subjects in the PP population and roll-in subjects treating the endpoint as a binary variable. The point estimate and the one-sided 95% exact binomial lower bound will be presented. The secondary effectiveness analysis will

also be performed in the Safety Population for all enrolled subjects who had study catheter inserted and RF delivered with study catheters.

Time to Event Analysis:

Time to event analysis will also be performed for these secondary effectiveness endpoints. Kaplan-Meier curves and survival estimates will be provided using data on all subjects in the PP population and roll-in subjects. The subjects who do not have effectiveness failures but are followed up less than the endpoint-specified evaluation periods will be censored at their last observations.

Subgroup Analysis:

In order to provide additional characterization and interpretation of the outcomes of 6-Month and 12-Month effectiveness success, subgroup analyses based on AAD history at baseline will be performed in the PP population.

For AAD history, subjects will be categorized into AAD refractory and the AAD naïve subgroups. The AAD refractory subgroup will consist of subjects who at any point prior to their enrollment received a Class I, II, III or IV AAD for treating AF. The AAD naïve subgroup will include subjects who never received any Class I to IV AADs prior to their enrollment.

The number and percentage of subjects with the secondary effectiveness endpoints will be presented in each subgroup. Kaplan-Meier estimates will also be presented by AAD history at baseline.

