### 8.3 Post-Ablation Follow-up Schedule

The subject will be required to complete follow-up visits through 12 months post initial ablation procedure. Follow-up will be done at 7 days (phone call or clinic visit), 1, 3, 6 and 12 months (clinic visit).

Discharged subjects will receive a telephone call or have a clinic visit at 7 days (7D, day 6-8) post ablation procedure to assess any occurrence of Primary Adverse Events; otherwise, in-hospital surveillance will capture any Primary Adverse Events.

Follow-up visits should be scheduled according to the following timeframes: 1 month (1M, day 23-37), 3 month (3M, day 76-104), 6 month (6M, day 150 - 210) and 12 month (12M, day 315-405). Follow-up visit schedule should be based on the date of the index study ablation procedure and will not reset if subject undergoes a repeat AF ablation procedure.

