1 STUDY DESIGN

This clinical investigation is a prospective, multicenter, single arm clinical evaluation utilizing the Biosense Webster Multi-Electrode Radiofrequency Balloon catheter and the Biosense Webster Multi-Electrode Circular Diagnostic catheter.

An adaptive Bayesian design [1] will be used to determine the sample size. A maximum of 230 evaluable subjects with symptomatic paroxysmal atrial fibrillation (PAF) may be enrolled in the main study phase. Subjects enrolled in the main study phase will be evaluated at 7 days, 1, 3, 6 and 12 months following the index procedures.

To minimize the learning curve effect on the evaluation of safety and effectiveness of the multi-electrode RF balloon catheter, the first 1 to 3 roll-in subjects will be assigned to each ablating physician in this study. Based on a maximum number of 20 sites, and assuming an average of 2 ablating physicians per site, up to an estimated 60 roll-in subjects will be included in the study.

A focused neuropathological evaluation will be integrated within the Main Study. A subset of subjects enrolled in the main study phase (40 subjects) will be included in the Neurological Assessment Evaluable (NAE) subgroup. Enrollment of NAE subjects may be terminated prior to achieving the target 40 subjects if study enrollment ends early after a planned interim look. NAE subjects will be assessed for incidences of symptomatic and asymptomatic pre-and post-ablation cerebral emboli with either an absence of CNS deficits (asymptomatic) or with emboli-associated neurological symptoms (symptomatic).

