6.2.2 Secondary Effectiveness Endpoints

- Percentage (%) of pulmonary vein isolation (PVI) touch-up by focal catheter among all targeted veins and by subject.
- Percentage (%) of subjects with use of focal catheter ablation for non-PV triggers
- 6-Month Documented Symptomatic AF Recurrence: Percentage (%) of subjects with freedom from documented, symptomatic atrial fibrillation (AF), atrial tachycardia (AT), or atypical (left side) atrial flutter (AFL) episodes (episodes >30 seconds on arrhythmia monitoring device from Day 91 to 180)
- 6-Month Documented AF Recurrence: Percentage (%) of subjects with freedom from documented, atrial fibrillation (AF), atrial tachycardia (AT), or atypical (left side) atrial

flutter (AFL) episodes (episodes >30 seconds on arrhythmia monitoring device from Day 91 to 180)

- 12-Month Documented Symptomatic AF Recurrence: Percentage (%) of subjects with freedom from documented, symptomatic atrial fibrillation (AF), atrial tachycardia (AT), or atypical (left side) atrial flutter (AFL) episodes (episodes >30 seconds on arrhythmia monitoring device from Day 91 to 365)
- 12-Month Documented AF Recurrence: Percentage (%) of subjects with freedom from documented, atrial fibrillation (AF), atrial tachycardia (AT), or atypical (left side) atrial flutter (AFL) episodes (episodes >30 seconds on arrhythmia monitoring device from Day 91 to 365)

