9 SAMPLE SIZE JUSTIFICATION

A Bayesian adaptive design will be utilized to select the final sample size of the trial. The sample size for the study is mainly driven by the primary safety endpoint. Sample size selection interim analyses will be performed when the mITT Population reaches 80, 130, and 180 subjects. Safety outcomes at 30 days will be used as a proxy for the primary safety endpoint at each

Biosense Webster, Inc

interim for determining the sample size. The predictive probabilities for the primary safety endpoint success will be used to determine whether the sample size at the time of the interim analysis will be sufficient or if the trial will continue to the full sample of 230. The final stopping sample size of 230 was determined by fixed design power calculations for the primary safety endpoint.

Trial simulations were performed to estimate the Type-I error rate and the power for the success of the safety endpoint under a range of assumptions for the true safety rate and the assumed enrollment schedule. It is assumed that the attrition rate for the study will be negligible. For accrual rates of 1.7, 3.4, 5.1, 8.5, 11.9, 17, 20.4, 23.8, 25.5, 25.5, 25.5, 25.5, 25.5, and 25.5 patients per month for months 1 to 15 respectively, and true safety rates of 0.0% to 9.0%, the power for showing success for the primary safety endpoint is estimated to be greater than or equal to 80.0%. For a safety rate of 9.5% this power decreases to approximately 73.0%. Based on the feasibility study results referenced in the study protocol, it is unlikely that the safety event rate is higher than 9.0%. The posterior probability of the safety rate being less than or equal to 9.0% is estimated to be 0.886. Therefore, the study is expected to be sufficiently powered for the primary safety endpoint. With an assumed true effectiveness rate of 96.0% and a performance goal of 80.0%, a minimum of 80 subjects will provide higher than 99.0% power for meeting the primary effectiveness endpoint. As a result, the power estimates for the primary safety endpoint closely estimate the overall power of the study.

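### The 6- and 12-month freedom rates carry a confidence bound only in their binary form, which on the natural reading drops event-free early leavers but keeps early failures; the planned Kaplan-Meier estimates have no bound.

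*SAP*

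**What the plan says.** SAP 6.2.2 defines four freedom endpoints: symptomatic and any documented AF, AT or atypical flutter, each over day 91 to 180 and over day 91 to 365. The 12-month versions count "episodes >30 seconds on arrhythmia monitoring device from Day 91 to 365".

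SAP 11.5 sets the rule for missing data: "Analyses of all secondary endpoints will be performed descriptively in the proposed analysis populations excluding the subjects with missing outcomes". It also sets the status of these endpoints: "No formal statistical hypothesis and inferential statistics will be formulated and performed for the secondary endpoints".

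SAP 11.5.2.1 then plans two analyses of the 6- and 12-month endpoints, both in the per-protocol population and in roll-in subjects:

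- A binary summary, "treating the endpoint as a binary variable. The point estimate and the one-sided 95% exact binomial lower bound will be presented". It is repeated in treated subjects of the Safety Population.
- Kaplan-Meier curves and survival estimates, in which "The subjects who do not have effectiveness failures but are followed up less than the endpoint-specified evaluation periods will be censored at their last observations". No confidence bound is mentioned for them.

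Protocol 14.8.6 also specifies an exact binomial lower bound at 180 and 365 days for symptomatic freedom, but in the mITT population.

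On dropout, SAP 9 says: "It is assumed that the attrition rate for the study will be negligible".

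**The concern.** A recurrence inside the evaluation period settles the endpoint. A subject who recurs on day 120 and leaves on day 150 is a known failure. A subject who is event-free when leaving on day 150 has no known day-365 outcome, so SAP 11.5 removes that subject from the binary analysis. Read this way, dropout takes only event-free subjects out of the denominator, and the proportion event-free falls.

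The Kaplan-Meier analysis treats the same subjects differently, because their event-free time counts up to censoring. Yet the binary rate is the only one of the two with a bound. At stake is how accurately the longer-term freedom rates are described. No success criterion of the study is affected.

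**Working it through.** **Stated figures.** Neither document gives an expected 6- or 12-month freedom rate, a dropout percentage or a precision target, so there is no figure of the plan to reproduce. Freedom and dropout below are assumptions.

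**Inputs.**
- Evaluation period for the 12-month endpoints: day 91 to 365, or 274 days (SAP 6.2.2).
- Bound: exact binomial, one-sided 95% (SAP 11.5.2.1).
- Sample size: "A maximum of 230 evaluable subjects with symptomatic paroxysmal atrial fibrillation (PAF) may be enrolled in the main study phase" (SAP 1). The per-protocol set may be smaller.
- Assumed: probability f = 0.25 of recurrence by day 365. A fraction d drops out, independently of outcome. Recurrence and dropout times are spread evenly over the period.

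**Binary rate on the natural reading.** Event-free completers are (1−f)(1−d). Observed failures are f(1−d/2), because a subject who both drops out and recurs does so in either order with equal chance. The rate is

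(1−f)(1−d) / [(1−f)(1−d) + f(1−d/2)].

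| d | Event-free completers | Observed failures | Binary rate | Error against 75.0% |
|---|---|---|---|---|
| 5% | 0.7125 | 0.2438 | 74.5% | −0.5 points |
| 10% | 0.6750 | 0.2375 | 74.0% | −1.0 points |
| 20% | 0.6000 | 0.2250 | 72.7% | −2.3 points |

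**Second model.** Use constant hazards, with true freedom S, lf = −ln S and ld = −ln(1−d). Observed failures are F = lf/(lf+ld) × [1 − exp(−(lf+ld))], completers are C = S(1−d), and the rate is C/(C+F). For S = 70% and d = 10%, C = 0.630 and F = 0.286, so the rate is 68.8% (−1.2 points). For S = 80% and d = 10% it is 79.1% (−0.9). For S = 70% and d = 2% it is 69.8% (−0.2). Direction and size agree with the table.

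**Effect on the bound.** Take N = 230, S = 70% and d = 10%. About 211 subjects remain, 145 of them event-free, and the exact lower bound is 63.1%. An undistorted 70% on the same 211 (148 event-free) gives 64.5%; no dropout (161/230) gives 64.6%. The bound falls by about 1.5 points, a small part of which is rounding to whole subjects.

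**The 6-month endpoints.** Day 91 to 180 is 89 of the 274 days, a fraction of 0.325. Scaling evenly from f = 0.25 and d = 10% gives f = 0.081 and d = 0.032. The formula returns 91.8% against a true 91.9%, an error of about 0.1 points.

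**Kaplan-Meier under the same conditions.** Simulated with N = 230 and independent dropout of 10%, its mean is 70.0% for S = 70% and 80.1% for S = 80%.

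**Informative dropout.** Let subjects who would later recur leave three times as fast (S = 70%, d = 10%). The binary rate is then 70.5% and Kaplan-Meier 71.3%. Both are too high, and Kaplan-Meier is further off.

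**Other readings of a missing outcome.** If everyone with incomplete follow-up is removed, failures included, there is no bias under independent dropout (70.0%). If event-free leavers count as successes, the rate is 71.4% at S = 70% and d = 10%.

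**The case against.** The best defence has four parts.

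- **The rule is inferred.** The SAP writes out the rule of keeping failures despite short follow-up only for primary safety (11.4.2 and 11.4.4). For the freedom endpoints it says only that missing outcomes are excluded, and other readings give no bias or an upward one. This stands, so the point is conditional on the natural reading. It is also a reason to define the term.
- **The effect is small and conservative.** With independent dropout up to 10%, the error is about 1 point. The binomial standard error at 75% and N = 230 is √(0.75 × 0.25/230) = 2.9 points. The error understates the device's performance, and the SAP expects negligible attrition. This stands too.
- **Kaplan-Meier is already planned.** Readers will see both figures, so what remains is a bound and a ranking. That is correct, and it is why the change is cheap.
- **Kaplan-Meier is not assumption-free.** The informative-dropout case shows this, so naming it the main estimate is not enough without a bounding analysis.

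A reader might infer that the binary rate is the plan's headline figure and that an effectiveness claim hangs on its bound. The documents do not support that. SAP 11.5.2.1 ranks neither analysis, the endpoints have no performance goal, and the effectiveness decision rests on acute procedural success (SAP 11.4.1).

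**Conclusion.** The point holds as a minor improvement. Its size rests on three assumptions: the natural reading of a missing outcome, dropout independent of outcome, and 75% true freedom at day 365. On these the 12-month rate is low by about 0.5, 1.0 and 2.3 points at 5%, 10% and 20% dropout. The bound falls with it, and the error is near zero if attrition is negligible. With informative dropout the sign can change, and Kaplan-Meier is biased as well. The documents therefore do not support a flat statement that the binary rate is biased low or that Kaplan-Meier is unbiased.

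A reader might also infer a much larger bias from the visit schedule. Protocol 8.3 lists "12 month (12M, day 315-405", so an event-free subject can complete the study up to 50 days before day 365. If such completers were treated as missing and made up 10% of subjects, the rate at S = 70% would be 67.9% with no dropout at all. But the documents neither say that these subjects are missing nor give the expected visit timing. This is a reason to state the rule, and it is not part of the size claimed here.

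**What to change.** In SAP 11.5.2.1:

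1. Report the planned Kaplan-Meier estimates at day 180 and day 365 with a one-sided 95% lower bound on the log-log scale, and name them the main estimate for the four freedom endpoints.
2. Keep the exact binomial rate and bound as supportive. State which subjects count as having a missing outcome, including those who recur and then leave and those whose 12-month visit falls before day 365.
3. Show the binary rate also with event-free dropouts counted as all failures and as all successes. In the worked case (f = 0.25, d = 10%) these dropouts are 1 − 0.675 − 0.2375 = 0.0875 of subjects, so the range is 67.5% to 76.3% (0.675 + 0.0875). This covers the case where dropout is informative.

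Align protocol 14.8.6 with the SAP on both the estimator (it specifies the exact binomial bound) and the population (mITT there, per-protocol in the SAP).

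Cost: no new data and one bound on an analysis already planned. The bound on the main estimate becomes asymptotic rather than exact, and the protocol text needs changing as well as the SAP.

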11.5.2.2 PVI and Non-PV Triggers Touch-Up with Focal Catheter

The number and percentage of subjects who have pulmonary vein isolation (PVI) touch-up by focal catheter among all targeted veins will be summarized with descriptive statistics. The number and percentage of PVs with touch-up by focal catheter among all targeted veins will be summarized with descriptive statistics.

The number and percentage of subjects who undergo ablation procedure using focal catheter for non-PV triggers will be summarized with descriptive statistics.

These analyses will be performed in the PP population and roll-in subjects.

11.5.3 NAE Endpoints

The occurrences of asymptomatic and symptomatic cerebral emboli will be summarized by timepoints of pre- and post-ablation procedure. Frequency, anatomic location, and size (diameter and volume) of cerebral emboli at baseline, post-ablation and during follow-up will also be

Biosense Webster, Inc

summarized. Neurologic deficits observed post ablation and during follow up period will be summarized.

The National Institutes of Health Stroke Scale (NIHSS) scores and Montreal Cognitive Assessment (MoCA) scores at baseline, post ablation and during follow-up will be summarized with descriptive statistics.

These analyses will be performed in the NAE population.

